#### 4.2 Exclusion Criteria

The exclusion criteria for enrollment into the registry (day 0-90) are: (none can be true)

- 4.2.1 Patients under 18 years old.
- 4.2.2 Patients who have an active unipolar pacemaker.
- 4.2.3 Patients with a physical or mental condition that could impair their ability to properly interact with the device.
- 4.2.4 Patients currently participating in an interventional clinical study.
- 4.2.5 Patients with any skin condition that would prevent wearing the device.
- 4.2.6 Patients with an advanced directive prohibiting resuscitation.

The exclusion criteria for enrollment into the study (day  $90 \pm 14$ ) are: (none can be true)

- 4.2.7 Patients under 18 years old.
- 4.2.8 Patients who have an active unipolar pacemaker.
- 4.2.9 Patients with a physical or mental condition that could impair their ability to properly interact with the device.
- 4.2.10 Patients currently participating in an interventional clinical study.

- 4.2.11 Patients with any skin condition that would prevent wearing the device.
- 4.2.12 Patients with an advanced directive prohibiting resuscitation.
- 4.2.13 Patients who have a QRS duration of ≥135 ms and are planned for cardiac resynchronization therapy during the study duration.
- 4.2.14 Patients with recent myocardial infarction or coronary revascularization (since start of WCD wear; i.e. 0-90 days of WCD wear).

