## 2 Study Objectives

## 2.1 Primary Objective(s)

The primary objective of this study is to observe the rate of recovery of ventricular function (EF>35%) between 90 and 180 days in newly diagnosed HF with reduced EF patients who were prescribed the WCD while being initiated on their HF medications. This will be measured from EF closest to before hospital discharge, then at 90, 180 and 360-days after WCD start, regardless of continued WCD use, prior EF improvement, or ICD implantation. While approximately one-third of the patients will likely experience EF recovery in the first 90 days, we hypothesize that an additional 5-10% of patients will experience EF improvement between 90 and 180 days as GDMT is achieved. This would be considered clinically significant in terms of the potentially avoided ICD implantations. Outcomes will be tracked and reported for three pre-specified groups based on assessment of SCD risk at 90 days of WCD use:

- 1) Patient improved (EF >35%), SCD risk deemed to be negligible. These patients are expected to end WCD use and not receive an ICD.
- 2) Patient improved EF from start of WCD use (a positive change of at least 5 percentage points in EF), or has a borderline EF of 30-35%, but still has continued SCD risk (EF ≤ 35%). These patients are expected to continue to use the WCD for an additional 3 months.
- 3) Patient not improved from start of WCD use (no change or worsening of EF), EF<30% and has continued high SCD risk. Those on GDMT are expected to be evaluated for an ICD. Those not yet on GDMT may continue the WCD for an additional 90 days.

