#### 3.2.2 LVEF recovery

To support our primary hypothesis that an additional 5% of patients will experience EF improvement between 90-180 days, EF measurement for all patients at 90 (±14), 180 (±14) and 360 (±14)-days after WCD start will be requested and recorded. For this study, EF>35% will be considered as EF improved.

- 3.2.2.1 Echocardiographic assessment of LVEF is most common. Nevertheless, other imaging modalities (MUGA, MRI) may be used to document LVEF at day 0. Although there are likely to be differences in EF assessment among enrolling sites and practices, these differences are not expected to affect the outcome of the trial. At a minimum, we will request a 2-D, M-mode echo at the scheduled time-points.
- 3.2.2.2 Echocardiogram core lab verification. EF is commonly estimated by echocardiogram. Several studies have shown EF measurement to have a wide range of variability that can be observer dependent. Study echocardiograms will be sent to a core lab for a uniform determination of the EF. The core lab determinations will be used to verify local estimates of EF and may be used in secondary analyses of the study data

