## 4 Study Subject

#### 4.1 Inclusion Criteria

The population for this study will be patients who had an ejection fraction (EF)  $\leq$  35% following hospitalization for newly diagnosed HF, and who have already been using a WCD for 90 days. Prior to 90 days, eligible patients will be enrolled into a registry. Registry patients will be enrolled during the first 30 days of WCD use.

All of the following must be true for enrollment into the registry (day 0 – 90 of WCD use):

- 4.1.1 Patients (≥18 years old) who were prescribed the WCD ≤ 10 days post-discharge after hospitalization for a primary reason of newly diagnosed HF with reduced EF (≤30 days since first HF hospitalization), with ischemic or nonischemic cardiomyopathy, and have used the WCD for no more than 30 days.
- 4.1.2 Patients who had an EF  $\leq$  35% during index hospitalization.

All of the following must be true for enrollment into the study (day  $90 \pm 14$ ):

- 4.1.3 Patients (≥18 years old) who were prescribed the WCD ≤ 10 days post-discharge after hospitalization for a primary reason of newly diagnosed HF with reduced EF (≤30 days since first HF hospitalization), with ischemic or nonischemic cardiomyopathy, and either 1) have already used a WCD for 90 ± 14 days or 2) were enrolled in the registry after 01-March-2019 and received an ICD prior to 90 days of WCD use.
- 4.1.4 Patients who had an EF  $\leq$  35% during index hospitalization. Of note, EF at 90  $\pm$  14 days post-hospitalization does not need to be low to be included in the study.

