## 8.3 Endpoint Assessment

## 8.3.1 Primary Endpoint – LVEF recovery and GDMT

Descriptive or summary statistics of serial EF measurements will be used to analyze the rate of recovery of ventricular dysfunction following discharge. For example, the means of EF at 180 days will be compared to the means of EF at baseline and 90 days. The percentage of patients reaching the goal of EF>35% will be compared at 90 days and 180 days. Also, the time taken to reach EF>35% will be calculated for those who improve, and compared between groups (based on baseline characteristics). Individual patient EF measurements over time will be compared to determine whether common patterns arise in certain groups of patients (fast recovery/slow recovery, plateaued recovery/peaked recovery followed by decline). The influence of baseline characteristics on the potential for recovery will be evaluated.

Descriptive statistics will be used to assess the degree GDMT was reached at 90 and 180 days, and how GDMT relates to EF recovery. We will also assess how adherence to the GDMT regimen affects EF recovery and overall clinical improvement.

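### Revascularization after day 90, and CRT outside the entry exclusion, are neither excluded nor handled in the analysis, so EF above 35% after either counts as late recovery on GDMT

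*Combined protocol and SAP*

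**What the plan says.** Two exclusions at day-90 entry concern procedures that can change EF (section 4.2). Item 4.2.13 removes "Patients who have a QRS duration of ≥135 ms and are planned for cardiac resynchronization therapy during the study duration". Item 4.2.14 removes "Patients with recent myocardial infarction or coronary revascularization (since start of WCD wear; i.e. 0-90 days of WCD wear". Ischemic cardiomyopathy is eligible (4.1.3). From March 2019 registry enrolment onward, so is a patient who "received an ICD prior to 90 days of WCD use".

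Recovery carries no condition on cause: "For this study, EF>35% will be considered as EF improved" (3.2.2). EF is read "regardless of continued WCD use, prior EF improvement, or ICD implantation" (2.1), and ICD recipients stay in follow-up (3.1.5, 5.4.1, 7.1). Section 3.1 states the hypothesis that further recovery comes between days 90 and 180 as GDMT is reached. Section 2.1 gives the value of such a gain: "This would be considered clinically significant in terms of the potentially avoided ICD implantations".

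For analysis, 8.3.1 says "The percentage of patients reaching the goal of EF>35% will be compared at 90 days and 180 days". Section 8.1.1 tests whether late improvement exceeds 5% of all patients, using the count among those who wear the WCD beyond day 90. Sections 8.4 to 8.6 add no rule on procedures after day 90. The follow-up list in 6.2.1.2 names ICD placement but neither CRT nor revascularization.

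**The concern.** The two exclusions suggest that the plan regards CRT, infarction and revascularization as reasons for EF change other than drug therapy. The protection has gaps in the very window on which the hypothesis rests:

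- Revascularization after day 90, planned or not, is outside 4.2.14.
- CRT decided after entry, or planned with QRS below 135 ms, is outside 4.2.13.
- CRT already implanted at entry is not clearly inside 4.2.13, which speaks of patients who "and are planned for cardiac resynchronization therapy during the study duration".

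Device decisions can fall in this window, because unimproved patients on GDMT are expected to be evaluated for an ICD at day 90 (2.1, group 3). If one of these procedures lifts EF above 35%, the patient adds to the late-recovery count that is then explained by GDMT. The error runs in favour of the hypothesis. Without a rule written in advance, who counts as recovered would be settled after the data are seen.

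**Working it through.** **1. The plan's own figure.** Inputs from 8.1.1: p = 0.23, p0 = 0.001, p_wcd = 1/3, margin 0.05/(1/3) = 0.15, so the null rate is 0.151; one-sided alpha 0.05; power 90%; follow-up 0.85 in each period.

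- Printed formula: n4 = 0.23 × 0.77 × [(1.645 + 1.282)/(0.23 − 0.151)]² = 243. Then n = 243 × 3/0.85² ≈ 1,010, which is not the stated 868.
- Exact one-sample binomial: n4 = 210, success at 41 or more (error 4.9%, power 90%). Then n = 210 × 3/0.85² = 872, within 0.5% of 868.

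I use the exact version. It agrees with the plan's flow: 868 × 0.85 = 738 at day 90; 738/3 = 246 extended wearers; 246 × 0.85 = 209 with a day-180 EF. The sizes were later recalculated, but the 200-250 extended wearers still targeted in 8.1 include this n4.

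**2. The planned margin.** Expected recoveries are 0.23 × 210 = 48.3 and 41 are needed. About 8 recoveries can therefore decide the result.

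**3. Recoveries affected.** The documents give no rate for either procedure. Assumption: a share q of 2-10% of extended wearers have one by day 180, and half of those cross 35%.

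| Base | After a procedure, q × 0.50 | Above the planned 23%, q × (0.50 − 0.23) |
|---|---|---|
| 246 at day 90 | 2.5 to 12.3 | 1.3 to 6.6 |
| 210 with day-180 EF | 2.1 to 10.5 | 1.1 to 5.7 |

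The right-hand column allows for the patients who would have recovered anyway at the planned rate.

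**4. Effect on the 5% test.** Suppose recovery without a procedure sits at the null, 15.1%. The observed rate is then 0.151 + q × (0.50 − 0.151), and the chance of 41 or more out of 210 is:

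| q | Rate | Chance of a positive result |
|---|---|---|
| 0 | 15.1% | 4.9% |
| 2% | 15.8% | 9% |
| 5% | 16.8% | 17% |
| 10% | 18.6% | 39% |

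**5. Price of the stricter count.** If the true rate without a procedure is 23%, and the share q is scored as not recovered whatever its EF, the rate becomes 0.23 × (1 − q). Power is 87% at q = 2% (rate 22.5%) and 69% at q = 10% (rate 20.7%), against 90% with no procedures.

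**The case against.** **CRT is excluded.** A reader might infer that CRT is left open altogether. It is not: planned CRT with QRS of at least 135 ms is excluded for the whole study duration, not only to day 90. The gap is confined to the routes listed above.

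**A CRT-defibrillator responder counts as an avoided ICD.** This is tempting but not supported. The avoided-implant remark in 2.1 is a rationale, and no count of avoided ICDs is defined. Section 4.1.3 speaks of an ICD without saying that a CRT-defibrillator qualifies. Early-device patients are also outside the n5/n4 proportion in 8.1.1 and would enter through the all-patient comparison in 8.3.1. For revascularization the argument fails altogether, since such a patient may still avoid an ICD.

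**Procedures could use up the whole planned margin.** One can set 492 unrecovered patients (738 × 2/3) × 8% × 0.5 = 19.7 against a margin of 56.6 − 36.9 = 19.7 (7.7% and 5% of 738). This mixes populations. The margin is built on the 246 extended wearers, while the 492 include patients who no longer wear the WCD.

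**Counting EF whatever happens is deliberate.** The study is observational, its objective is to observe recovery, and 8.3.1 examines the GDMT link separately and descriptively. This stands, so the measured rate should remain the observed result. It does not settle what may be attributed to GDMT.

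**The data may already exist.** Reasons for hospitalization are collected (3.3.4, section 9), ICD placement is recorded, and the CRF is a separate document. The Clinical Status row of Table 2 is also incomplete in the text available. Absence from these lists does not prove absence from the CRF, but later separation would still not be pre-specified.

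**Conclusion.** The gap is real but limited. Revascularization after day 90, and CRT unplanned at entry or planned with QRS below 135 ms, are neither excluded nor handled. CRT already implanted at entry is unclear. Any EF above 35% that follows counts as late recovery attributed to GDMT.

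The size cannot be set from the documents. It rests on two assumptions (2-10% with a procedure, half crossing 35%) and on the exact test that comes closest to 868. At the low end the effect is small. At the high end the recoveries above plan come near to, but do not reach, the roughly 8 that could decide a result at the planned rate, while the one-sided error at the null becomes serious. Severity is moderate: the observed recovery rate stands as a description, and only its attribution to GDMT is exposed.

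**What to change.** 1. In the Clinical Status item of Table 2, record CRT and coronary revascularization, each with its date, or confirm that the CRF already does.
2. Keep the as-measured percentage with EF above 35% as the observed recovery rate.
3. In 8.3.1 and 8.1.1, pre-specify a supporting analysis of the 5% claim: patients with either procedure between WCD start and the day-180 echo stay in the denominator but are not counted as recovered on GDMT. This count is conservative, since some would have recovered anyway.
4. Limit the conclusion about recovery on GDMT to results that hold in both analyses.
5. State whether 4.2.13 covers CRT already implanted at entry.

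The cost is two chart-review fields and a few lines of analysis text. The downside is a possibly lower GDMT-attributed figure and, under the assumptions above, some loss of power in the supporting analysis.

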## 5 Study Enrollment Plan

## 5.1 Enrollment Strategy

Investigators and sites will be identified based upon site-initiated interest in the study, sites that have adequate HF patient volumes, and through sponsor-identified research sites that are currently high prescribers of the WCD for HF patients. Some investigators may be identified through an Institutional Review Board (IRB) database service.

Patient enrollment strategies may be targeted at both the investigator and the patient as a way to engage all interested parties and provide informational materials for the study. Strategies may include patient and/or investigator focus groups, educational lectures, web sites, or flyers, or study coordinator brochures to assist in the recruitment and screening process.

## 5.2 Study Size

Up to 1400 subjects will be enrolled into the pre-study registry, and up to 600 may be enrolled in the study portion. Thirty to eighty sites will enroll patients into the study. Sites will initially be located in the United States and Germany, but may be expanded to other European countries. Individual sites will only be allowed to enroll up to 140 patients (or 10% of the total population).

#### 5.3 Enrollment Period

This study is expected to finish enrollment within 48 months after the start of enrollment.

### 5.4 Early Withdrawal of Subjects

### 5.4.1 When and How to Withdraw Subjects

All patients enrolled into the study can withdraw at any time regardless of the reason. Patients may withdraw consent for use of data and exit the study at any time without prejudice to further treatment.

Patients who receive an ICD versus continuing WCD as described by the protocol will not be considered withdrawn from the study, and will continue to be followed.

Patients who refuse an ICD or WCD continuation as described by the protocol will not be considered withdrawn from the study, and will continue to be followed.

#### 5.4.2 Data Collection and Follow-up for Withdrawn Subjects

When a subject withdraws from participating in the study, this will be documented, and the already collected data will remain part of the study and will be used in data analysis. The reason for withdrawal from the study will also be documented, if known. If the patient agrees, a follow-up phone call to assess mortality only may still be made.

In the case of patients who are lost to follow-up, all pre-existing study data on the patient will still be used.

## 6 Study Procedures

## 6.1 Subject Recruitment and Screening

### 6.1.1 Subject screening for WCD registry and study

Patients will initially be screened from the prescribed WCD patients and enrolled into the prestudy registry. At 90  $\pm$  14 of WCD use, study subjects will be identified and screened from the clinical site's pre-study registry participants. The sponsor may also assist in the screening process by maintaining a current list of WCD prescribed patients to be screened for the registry by each site. Registry participation is complete when the patient enters the HF Opt study, or ends WCD use.

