## 2.3 Safety Objective(s)

The safety objectives will be to compare complications from extended use of the WCD with those of the ICD during the study timeframe.

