## 3 Study Design

## 3.1 General Design

This study is designed as a multi-center prospective observational study of newly diagnosed HF with reduced EF patients to test the hypothesis that additional EF recovery occurs between 90 and 180 days as GDMT is achieved. Although the study doesn't start until day 90, all eligible, consenting patients will be entered into a registry at the start of WCD use. The pre-study registry will allow us to collect early (90 day) outcomes and data in those patients who are likely to be eligible for the study at day 90, or are eligible, but refuse the study at day 90.

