#### 3.1.3 Expected Duration of Study Participation

The anticipated length of active study participation is 12 months from the start of WCD use.

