#### Serious injury

Serious adverse device effects include any injury or event that is:

- Fatal or life-threatening, or
- Requiring or prolonging hospitalization, or
- Resulting in permanent impairment of a body function or permanent damage to body structure
- Necessitates medical or surgical intervention to preclude permanent impairment of a body function or permanent damage to a body structure

The Investigator should also assess whether the adverse device effect is anticipated or unanticipated.

At each contact with the subject, the investigator must seek information on adverse device effects by specific questioning and, as appropriate, by examination. Information on all adverse device effects should be recorded immediately in the source document, and also in the appropriate adverse effect module of the CRF. All clearly related signs, symptoms, and abnormal diagnostic procedures results should recorded in the source document, though should be grouped under one diagnosis.

All adverse device effects occurring during the study period must be recorded. The clinical course of each event should be followed until resolution, stabilization, or until it has been determined that the study treatment or participation is not the cause. Serious adverse device effects that are still ongoing at the end of the study period must be followed up to determine the final outcome. Any serious adverse device effects that occur after the study period should be recorded and reported promptly.

The minimum initial information to be captured in the subject's source document concerning the adverse device effect includes:

- Study identifier
- Study Center
- Subject number
- Device model and serial number
- A description of the event
- Date of onset

- Investigator assessment of the association between the event and study treatment
- Current status
- Whether study treatment was discontinued
- Whether the event is serious and reason for classification as serious

Serious adverse device effects should be reported to ZOLL immediately. The ZOLL contact persons for this study are:

In the United States:

[name], Clinical Research Project Manager [name] (office phone) [name] (fax) [contact] (email)

In Europe:

[name], Clinical Operations Manager EMEA [name] (office phone) [contact] (email)

The reviewing ethics committee must also be notified within 10 working days.

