## 11 Administrative Responsibilities

## 11.1 Sponsor

ZOLL, the Sponsor, is responsible for study administration as well as providing devices and related materials for the study. The Sponsor will select appropriate investigators, assure collection of investigator agreements, assure IRB approval of the protocol, and monitor informed consent records.

The sponsor may also assist in the screening process by maintaining a current list of eligible patients to be screened by each site (i.e., those patients who are still active WCD users at day 90  $\pm$  14).

The Sponsor will designate appropriately trained and qualified individuals to monitor the investigation. These individuals will verify the adherence to procedures specified in the protocol, and verify maintenance of required subject and data records.

The Sponsor will provide trained and qualified individuals to fit subjects with the WCD and to provide training on the use of the WCD.

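### For an ICD implanted before day 90, no scheduled contact covers the time from implant to study entry, so complications of early implants may be under-captured in the safety comparison

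*Combined protocol and SAP*

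**What the plan says.** The only safety objective (2.3, repeated in 3.4) is to "compare complications from extended use of the WCD with those of the ICD during the study timeframe". Section 3.4.1 defines the ICD side as complications in those who receive an ICD, including inappropriate interventions and events that may lead to hospitalization or death. Section 8.3.7 analyses both devices descriptively.

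Follow-up is in two parts. The registry runs from WCD start, and under 6.1.1 "Registry participation is complete when the patient enters the HF Opt study, or ends WCD use". On the study itself, 3.1 says that "the study doesn't start until day 90". Besides patients with about 90 days of WCD use, 4.1.3 admits those who "were enrolled in the registry after 01-March-2019 and received an ICD prior to 90 days of WCD use". Consent for the study is taken at the day 90 ± 14 visit (6.1.3, 6.2.3).

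On recording of events, 10.2.1 says: "All adverse device effects occurring during the study period must be recorded". On the length of participation, 3.1.3 says: "The anticipated length of active study participation is 12 months from the start of WCD use".

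**The concern.** The second entry route in 4.1.3 places early ICD recipients on the ICD side of the safety comparison. Nothing matching it was added to the registry stopping rule or to the Visit 1 list. These patients join at about day 90, after the implant and the weeks that follow it, and only if they are alive and willing to consent.

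For ICDs placed after study entry, the implant and its aftermath fall within scheduled follow-up. The ICD side would therefore mix patients observed from implant with patients observed from some weeks after it. Events that were not collected cannot be restored in analysis, and 8.6.3.2 rules out replacing missing data. The gap also works against the registry's purpose as stated in 3.1, which is to collect early, 90-day outcomes, including from patients who decline the study.

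**Working it through.** The plan gives no figure to reproduce: no ICD complication rate, no expected number of ICDs before day 90, and no sample size for the safety comparison. The check is a reading of the follow-up rules.

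**1. Length of the gap.** Study entry is at day 90 ± 14, that is, day 90 − 14 = 76 to day 90 + 14 = 104. If the ICD ends WCD use on day d, registry participation ends on day d, and the interval to study entry is between 76 − d and 104 − d days. For an illustrative implant on day 40, that is 36 to 64 days.

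**2. What the registry collects.** Table 1 has two time points: the initial visit (days 0–30) and WCD end. At WCD end it takes medications, the reason for stopping, compliance and WCD defibrillation data. It has no row for ICD complications and none for survival after WCD end.

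**3. Unscheduled contacts.** Section 6.3 covers registry patients and includes device and adverse-event information. It says such visits may occur, the relevant trigger is an unanticipated end of WCD use, and the timing is immediately after notification. A contact triggered by the implant precedes any later complication. Death is also a trigger, but under 6.1.1 the patient's registry participation is by then complete.

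**4. What day 90 collects.**

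| Source | Captured at day 90 | Not stated |
|---|---|---|
| 6.2.1.2 | ER visits, HF hospitalizations, survival and ICD placement, by chart review and interview | ICD complications; a look-back period |
| Table 2 | ICD or WCD defibrillation data; care utilization; ICD implantation | A look-back to implant |
| 6.2.3 (Visit 1) | Clinical data, echo, ECG, medications | The device, adverse-event and cardiac-event item listed at days 120/150, 180, 270 and 360 |
| 10.2.1 | Questioning on adverse device effects at each contact; onset date | Whether ICD effects are covered (the lists in 10.1 concern WCD wear); the start of the study period |

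**5. Start of the safety window.** Neither the timeframe in 2.3 nor the study period in 10.2.1 has a start day. Section 3.1 points to day 90. Section 3.1.3 counts from WCD start, and 8.3.4 analyses SCA from the beginning of WCD use. The text supports either reading.

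**6. Who is missing.** Early ICD recipients who die or decline before consent do not enter the study. Those who joined the registry on or before 01-March-2019 do not qualify through the early-ICD route. Both groups drop out of numerator and denominator.

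**7. Size.** Among ICD patients who do enter, and with equal risk per patient assumed, the share of their complications missed is f × s × (1 − c). Here f is the share implanted before day 90, s is the share of such a patient's complications that arise between implant and day 90, and c is the share of those recovered at WCD end or by day-90 review. The documents give none of the three. With assumed ranges of f = 0.10–0.50 and s = 0.25–0.75:

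- c = 0: 0.10 × 0.25 = 2.5% to 0.50 × 0.75 = 37.5%
- c = 0.5: half of that, 1.25% to 18.75%
- c = 1: 0%

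This shows only that the answer depends on unstated inputs, above all c. It is not an estimate for this study.

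**The case against.** The strongest reply is that day-90 capture is better than the Visit 1 list suggests. Table 2 marks defibrillation data and care utilization, a chart can reach back, and 10.2.1 requires specific questioning and an onset date. Together these cover much of what 3.4.1 asks for in patients who enter. The CRFs and consent form are not in the documents, so a look-back may already be built in. This stands, and it limits the point to capture that is unspecified rather than absent. It does not help patients who never enter.

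A reader might infer that the implant period of early ICDs is always outside the safety window. The documents do not support that: the window's start is undefined, and 3.1.3 allows a count from WCD start.

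A reader might also infer that ICD complications are understated relative to the WCD. That is not shown. The comparator is extended WCD use, which also requires the patient to reach about day 90, and the documents give no time pattern of complications for either device.

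Finally, a reader might see the sponsor's screening list in 11.1, limited to "those patients who are still active WCD users at day 90", as a barrier to early ICD recipients. That list is optional help. Under 6.1.1 sites screen from their own registry participants.

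**Conclusion.** The point holds in limited form. Under the rules as written, the time from an early ICD implant to study entry has no scheduled contact. Entry selects patients who survived and consented, and no look-back to implant is stated. ICD complications from early implants may be under-captured. ICDs placed after study entry are not affected.

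The size cannot be derived from the documents, and the direction of any effect on the comparison with extended WCD use is not established. The conclusion assumes that an ICD implant ends WCD use and that the CRFs do not already require a look-back. Because the safety analysis is descriptive, with no test or margin, no formal decision turns on this. It is a worthwhile, low-cost correction to the only safety comparison in the plan.

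**What to change.** 1. In 2.3 and 3.4, state when the safety window starts for each device, with ICD complications counted from implant, and reconcile 3.1 with 3.1.3.
2. Add to Visit 1 (6.2.3) the device, adverse-event and cardiac-event item already used from day 120, with a look-back to the implant date.
3. Amend 6.1.1 so that registry participation runs to day 90 after an early ICD. Where the registry consent allows, take vital status and ICD complications from the chart, including for patients who die or decline study entry.
4. Report ICD complications separately for implants before and after study entry, so that any remaining gap is visible.

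The cost is protocol and CRF wording, one look-back at an existing visit, a chart check for a minority of registry patients, and possibly a change to the consent wording. The consent form is not in the documents, so the extent of that last change cannot be judged here.
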